# TRIAL SUMMARY

Trial Title	Acetazolamide as a chloride sparing Diuretic in patients Admitted with Heart Failure: a pilot study					
Internal ref. no. (or short title)	ADA-HF					
Clinical Phase	Phase II					
Trial Design	Open label, randomised, controlled, pilot and exploratory study.					
Trial Participants	Patients admitted to Castle Hill Hospital with venous congestion due to heart failure who are deemed to require a continuous intravenous infusion (IVI) of furosemide at (10mg/hr) – standard of care for severe venous congestion.					
Planned Sample Size	40 (maximum recruitment of 50)					
Treatment duration	4 days					
Follow up duration	180 days					
Planned Trial Period	30 weeks					
Primary Objective	1) Difference in net fluid loss daily and over a 4 day period					
	2) Difference in serum chloride between baseline and day 4					
Secondary Objective	Differences between the two groups during the 4 day treatment period in:					
	1) daily urine output					
	2) daily weight					
	3) serum electrolyte levels (sodium, bicarbonate and potassium)					
	4) incidence of electrolyte abnormalities; hyponatraemia (<135 mmol/L), hypochloraemia (<96 mmol/L), hypokalaemia (<3.5 mmol/L), high (>30 mmol/L) or low (<22 mmol/L) serum bicarbonate.					
	5) change in renal function measured by serum creatinine (µmol/L) and estimated glomerular filtration rate (eGFR) (ml/min/1.72m2)					
	6) change in urinary electrolyte levels after 48 and 96 hours of treatment; sodium, chloride, potassium.					
	7) clinical assessment of congestion					
	8) ultrasound measures of congestion period; inferior vena cava (IVC) diameter.					
	9) change in breathlessness score using the Likert scale.					
	10) time to clinical euvolaemia and end of intravenous therapy					
	11) length of stay					
	12) rate of adverse events related to acetazolamide – treatment arm only					
	13) rate of adverse events					

Hull University Teaching Hospitals

	NHS T					
	14) Tate of recruitment to study					
	15) time taken to screen & recruit					
	16) rate of drop-out after randomisation – cause specific					
	17) Cause specific hospitalisation or mortality after 30 days and 180 days follow up.					
Investigational Medicinal Product(s)	Acetazolamide					
Formulation, Dose, Route of Administration	Tablet. 250mg twice daily. Oral.					
	Inclusion					
Main inclusion/exclusion	
 
Aged ≥18 of any gender
 
					
criteria	2) Able to give informed written consent to participate in the trial					

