# 2.2 Assessment and management of risk

The British National Formulary lists the common or very common side effects of acetazolamide to be: ataxia, depression, diarrhoea, dizziness, fatigue, flushing, irritability, headache, loss of appetite, nausea, vomiting, taste disturbance, parasthesiae, reduced libido, polyuria, and thirst. Notable uncommon side effects include: metabolic acidosis, electrolyte disturbances, blood disorders, skin rashes and symptoms consistent with renal calculi.

The early studies suggested that side effects such as drowsiness and paraesthesia are seen in 14-38% of patients with heart failure at doses >1000mg per day, although side-effects were less common at doses ≤500mg per day (5-10%). Modern day studies did not report any adverse events but it is not explicitly stated that this is due to the medication being well tolerated.

We judge the above side effects to be of low clinical risk to the patient however it is possible a patient experiencing any one of the those side effects after starting acetazolamide may wish to end their participation. This, in itself, would be a useful endpoint. One of the many unknowns about acetazolamide in contemporaneous studies is the tolerability used either in isolation or in conjunction with high dose loop diuretic.

There are potential risks to the patient from the combination of acetazolamide and high-dose loop diuretic treatment, however we are unable to estimate their expected frequency: 1) increased risk of hyponatraemia – as both medications increase urinary sodium excretion; 2) increased risk of symptomatic hypotension due to increased intravascular volume loss and 3) increased risk of renal dysfunction. Daily assessment of urine and serum electrolytes and the patient will detect any changes that might be associated with increased risk to the patient and these will be discussed with the patient regarding continuation. Again, this would be a useful endpoint in itself regarding tolerability of the combination of diuretics. Furthermore, worsening electrolyte abnormalities, symptomatic hypotension and worsening renal function would be expected in the standard care arm also.

Ultimately we would expect all treatment related adverse events to resolve upon withdrawal of the study treatment should the patient wish to do so or if the risk to the patient was felt too great to allow their continuation in the study.

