# 7.3.1 Method of implementing the allocation sequence

Randomisation will be performed by the Simple Randomisation Service offered by Sealed Envelope TM (https://www.sealedenvelope.com). Patients will be randomised 1:1 to either A – acetazolamide or B – standard of care in a random permuted block of up to 50 patients (maximum recruitment). Randomisation will be accessed by the study doctors and the sponsors but randomisation will be performed by the study doctors at the point of consent. Sealed Envelope confirms allocation via email to the person performing the randomisation, a copy of which will also be sent to a member of the Research and Development team who will print the email and include in the CRF. The CI ([name]) can be contacted in an emergency via phone.

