# Net fluid loss

Current guidelines recommend a target of ~1000ml net fluid loss per day during in-patient diuresis, which generally occurs over a period of up to 9 days (median length of stay for a patient hospitalised with heart failure in the UK). We estimate that a clinically significant difference in daily net fluid loss is 500-1000 ml – a minimum of 4.5L over a 9 day period and 2L over the 4 day period of our study. Such an increase in net fluid loss would indicate a significant increase in diuresis that may shorten hospital admission.

Using the available data on urine output (appendix 7), we expect an average daily fluid loss of 1000ml per day with a standard deviation ranging from 500-1000ml. Patients admitted with heart failure are often breathless on very modest exertion thus we anticipate a drop-out rate of 10% in the control arm. Furthermore, given the lack of reliable clinical data on the tolerability of acetazolamide we have anticipated a higher drop-out rate of 20% in the acetazolamide arm. Thus, to detect a difference of

500-1000ml in net fluid loss per day with statistical power of 80% and two-tailed significance of 5% we would need to recruit a minimum of 35 patients (17 in the control arm and 18 in the acetazolamide arm).

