# Serum chloride concentrations

Low serum chloride is associated with adverse outcome in patients with HF. We estimate a clinically meaningful change in chloride to be -0.9 mmol/L per day over the course of an admission (9 days) and -3.6 mmol/L over the four day period of our study (appendix 7). To detect such a difference with 80% power and 5% two-tailed significant with the above anticipated drop out rate we would need to recruit a minimum of 14 patients in the control arm and 17 patients in the ACZ arm.

We expect two potential confounding factors for the co-primary endpoints: 1) daily salt intake and 2) loss of IV access reducing the amount of IV furosemide given. We will collect data on both potential confounders using a daily dietary sheet (on which the patient will record their meals for the day and from which the daily salt intake will be estimated) and recording the "number of hours of furosemide" per day. We do not expect any patient to have excessive salt intake (defined by the European Society of Cardiology Heart Failure Guidelines 2021 as >5g per day). Any patient with >5g salt intake per day or <20 hours of furosemide per day will be removed from the analysis. Due to the exploratory nature of the study we will conduct an intention to treat analysis and a per-protocol analysis in which only patients who completed the study without deviating from the protocol will be included. Thus, we will recruit a maximum of 50 patients – 23 in the control arm and 27 in the ACZ arm with anticipated drop out of 10% and 20% respectively. The extra patients recruited will also act as a contingency should any patient need to be removed from the analyses for reasons of excess salt intake, prolonged loss of IV access, or for the per-protocol analysis.

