# 10.3.3 Secondary outcome analysis

Secondary outcomes are exploratory and none are powered for statistical significance. Secondary outcomes that are measured as continuous variables (difference in daily urine output; difference in weight from baseline to day 4; difference in change in serum sodium potassium, bicarbonate, urea, creatinine, and estimated glomerular filtration rate between baseline and day 4; urinary electrolyte concentrations at day 2 and day 4; inferior vena cava diameter; change in breathlessness score (Likert scale); time to clinical euvolaemia; and length of stay) will be assessed using independent samples t-test, and unadjusted linear regression (with treatment assignment as the independent variable), and linear regression adjusted for daily salt intake and median number of hours of furosemide per day.

Secondary outcomes that are measured as categorical variables (incidence of hyponatraemia, hypochloraemia, hypokalaemia, metabolic alkalosis (serum bicarbonate concentrations >29 mmol/L) or metabolic alkalosis (serum bicarbonate concentrations <23 mmol/L); clinical assessment of congestion; proportion of patients with IVC diameter >2cm; proportion of patients with JVD ratio <4; rate of adverse and serious adverse events; rate of drop-out after randomisation will be assessed using chi-squared tests, un-adjusted logistic regression (with treatment assignment as the independent variable), and logistic regression adjusted for daily salt intake and median number of hours of furosemide per day.

Survival analysis (time to cause specific hospitalisation and time to cause specific mortality) will be conducted with a time-to-first event analysis using Kaplan-Meier and logrank tests, un-adjusted Cox proportional-hazard outcome models.

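### For sparse binary outcomes at about 20 per arm, the maximum-likelihood logistic models in section 10.3.3 are unstable and sometimes have no finite odds ratio

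*Protocol*

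**What the plan says.** Protocol section 10.3.3 sets one method for all categorical secondary outcomes. They "will be assessed using chi-squared tests, un-adjusted logistic regression (with treatment assignment as the independent variable", followed by logistic regression adjusted for salt intake and furosemide hours. The list mixes electrolyte abnormalities, clinical congestion, IVC diameter above 2 cm, adverse and serious adverse events, and drop-out. It gives no rule for small counts. Section 3.5 adds that drop-out is to be cause specific.

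The trial summary plans "40 (maximum recruitment of 50" patients, and section 7.3.1 states "Patients will be randomised 1:1 to either A". The chloride part of section 10.1 says "we will recruit a maximum of 50 patients – 23 in the control arm and 27 in the ACZ arm". Its net fluid loss part assumes drop-out of 10% in the control arm and 20% in the acetazolamide arm. On tolerability, section 2.2 says of early acetazolamide studies that "side-effects were less common at doses ≤500mg per day (5-10" per cent.

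Section 10.3.3 also calls the secondary outcomes exploratory and unpowered. Section 4 nevertheless makes feasibility and tolerability data the primary aim, to inform a larger study.

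**The concern.** A maximum-likelihood odds ratio for treatment is finite only if both arms contain at least one event and at least one non-event. With few events, one arm can easily have none. Even when the estimate exists, a model with three slopes fitted to a handful of events is unstable. Drop-out and adverse events are among the results that the larger trial would be built on. If the planned model gives an infinite or erratic odds ratio for them, the report carries nothing from that model that a designer can use.

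**Working it through.** The protocol states no event rate, count or power for any binary comparison, so there is no figure of its own to reproduce. The check takes its stated sizes and rates and asks how often the planned model can be fitted.

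**Inputs**
- Arms: 20 and 20 (planned total of 40 at 1:1), or 23 and 27 (maximum, section 10.1).
- Drop-out: 10% and 20% (section 10.1).
- Side-effect rate: 5-10% (section 2.2). It is stated for acetazolamide only, so using it in both arms is an assumption.
- Slopes in the adjusted model: treatment, salt intake, furosemide hours, so three.

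**Events at the drop-out rates, 20/20**
- Expected events: 20 × 0.10 + 20 × 0.20 = 6, or 6 / 3 = 2 per slope.
- The smallest expected cell count is half the total number of events, so reaching 5 takes 10 events (10 / 40 = 25% pooled).
- Summing the binomial probabilities of all tables with fewer than 10 events gives 93.5%.
- At 23/27, expected events are 23 × 0.10 + 27 × 0.20 = 7.7, or 2.6 per slope.

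**Chance that the unadjusted odds ratio is not finite**

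This is 1 − [1 − (1 − p₁)^n₁] × [1 − (1 − p₂)^n₂]; the terms for an arm made up entirely of events are negligible here. For drop-out at 20/20: 0.90^20 = 0.122 and 0.80^20 = 0.012, so 1 − 0.878 × 0.988 = 0.13.

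| Rates | 20/20 | 23/27 | Basis |
|---|---|---|---|
| 10% / 20% | 13% | 9% | protocol's drop-out rates |
| 10% / 10% | 23% | 14% | assumption |
| 5% / 10% | 44% | 35% | assumption |
| 5% / 5% | 59% | 48% | assumption |
| 20% / 20% | 2% | 1% | assumption |

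**Adjusted model.** In 600 simulated trials per setting at 20/20, with two independent continuous covariates assumed, no finite fit existed in 11% (10%/20%), 23% (10%/10%), 43% (5%/10%) and 58% (5%/5%). Apart from simulation error these match the unadjusted figures. Adjustment does not rescue the model, and it spreads the few events over more parameters.

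**Subgroups.** Section 10.4 repeats all endpoints by sex and by age. At about 10 per arm and the drop-out rates, 0.90^10 = 0.349 and 0.80^10 = 0.107, so 1 − 0.651 × 0.893 = 0.42 have no finite odds ratio.

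**Tests.** By exact enumeration at 20/20, the two-sided 5% size at true rates of 5%, 10% and 20% is:
- uncorrected chi-squared: 0.012, 0.039, 0.050
- Fisher's exact test: 0.002, 0.012, 0.023

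For 10% against 20%, power is 14% by chi-squared and 7% by Fisher's test.

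**What stays estimable.** Take 2/20 against 4/20. The Wilson limits are 2.8% to 30.1% and 8.1% to 41.6%. The risk difference is +10 points. Newcombe's limits are 10 − √(11.9² + 20.1²) = −13 and 10 + √(21.6² + 7.2²) = +33 points. With 0/20 against 4/20 the odds ratio is infinite, but the counts and the difference of 20 points remain.

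**The case against.** Three stronger readings are tempting, and the protocol supports none of them.

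First, that the whole categorical list is affected. Section 2 calls hypochloraemia common. Hyponatraemia is defined as below 135 mmol/L while entry is allowed from 130. Congestion and a wide IVC are likely in patients admitted for congestion. The definition of serious adverse events in section 9.2 is broad. At an assumed 30% per arm, an expected count falls below 5 in only 20% of trials at 20/20, and the odds ratio is almost always finite.

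Second, that the 23-59% range is what the protocol predicts. The 5-10% figure concerns acetazolamide side effects, and reactions to acetazolamide are a treatment-arm outcome in section 3.5. Using it for both arms shows a range and is not the plan's own assumption. On the stated drop-out rates the figure is 13% or 9%, which is not most of the time.

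Third, that the chi-squared test would produce false positives. Its exact size is at or below nominal at the rates checked, while Fisher's test roughly halves the power. Exchanging one for the other is largely preference.

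It is also fair that counts and percentages per arm exist whatever the model does, that interval reporting may be set out in a SAP, and that the outcomes are exploratory. All of this limits the weight of the point. It leaves one thing standing: the protocol itself prescribes the logistic models without exception, and exploratory status excuses low power, not a model that cannot be fitted.

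**Conclusion.** The point holds for sparse outcomes only: individual adverse events, serious adverse events if infrequent, and drop-out, particularly by cause. At the protocol's drop-out rates and 20 per arm, the adjusted model has about 2 events per slope and the odds ratio is not finite in 13% of trials (9% at 23/27). If rates are 5-10% in both arms, that becomes 23-59% at 20/20. These figures assume independent patients and the stated arm sizes; splitting drop-out by cause makes them worse. The consequence is modest. No primary conclusion depends on these models and simple rates survive, but drop-out and tolerability are what the pilot is meant to hand on.

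**What to change.** Amend section 10.3.3. For any binary outcome with an expected cell count below 5, make the main result the counts per arm and the risk difference with a Newcombe or exact 95% interval. For those outcomes drop the covariate-adjusted logistic model, or fit Firth's penalised likelihood with treatment as the only term. If a p-value is wanted, use a mid-P or other small-sample test; Fisher's test is optional, because it is markedly conservative here (size 0.002 to 0.023). The planned methods can stay for frequent outcomes.

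The change is one of wording and needs no extra data or patients. What is lost is the covariate-adjusted odds ratio for sparse outcomes.

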# 10.4 Subgroup analyses

Subgroup analyses for all endpoints on sex and age (above and below median value).

# 10.5 Interim analysis

No planned interim analysis

# 10.6 Subject population

As this is a pilot and exploratory study, we will perform both an intention to treat analysis on all patients completing the study so that we can most accurate describe the clinical effects of ACZ including tolerability and side effects and a per-protocol analysis so we can most accurately assess the primary endpoints.

# 10.7 Procedure(s) to account for missing or spurious data

We will attempt to replace any patient with data missing for either primary endpoint (i.e. those who did not complete 4 days of treatment, those with data on net fluid loss missing on any day, and those with data on serum chloride missing on baseline or day 4). However, we expect missing data to be a minor problem as data collection for net fluid loss will be done by the study team during each visit and data on chloride concentrations will be collected as part of routine care. Reasons for missing data will be recorded in a dedicated section within the CRF for each study visit. We will not perform any imputation of missing data.

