# 3.4 **Primary endpoint/outcome**

Difference in mean net fluid loss daily and over a 4 day period

• Total volume intake in millilitres (mL) – total volume passed as urine in mL

Difference in serum chloride concentrations between day 1 and day 4

• Serum chloride day 4 – serum chloride day 1

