# 10.3.2 Primary outcome analysis

# Primary outcomes

We will calculate the median net fluid loss each day and from baseline to day 4 for patients in the ACZ arm and the control arm. We will assess distribution of daily and total fluid loss in both arms, if there is normal distribution we will compare the median net fluid loss using independent samples T-test, if the distribution is not normal we will use the Mann-Witney-U test. A P value <0.05 will indicate a statistically significant difference between the two arms. We will also perform linear regression with total net fluid loss from day 1 to day 4 as the dependent variable and treatment assignment, median daily salt intake and median number of hours of furosemide per day as the independent variables.

We will calculate the median change in serum chloride concentrations between the two groups between baseline and day 4. We will compare the median change in serum chloride concentration using independent samples T test. We will also perform linear regression with total change in serum chloride levels day 1 to day 4 as the dependent variable and treatment assignment, median daily salt intake, and median number of hours of furosemide per day as the independent variables.

The independent samples T test assumes that both net fluid loss (daily and total) and change in serum chloride concentrations between day 1 and day 4 are normally distributed in both groups; this will be tested using distribution curves. It also assumes that there is equal variance in both net fluid loss (daily and total) and change in serum chloride concentrations between day 1 and day 4; this will be tested using Levene's test, the samples will be assumed to have equal variance if Levene's test is P>0.05.

We do not expect any missing data, however any patient with missing data for each of the co-primary endpoints will be excluded from the analysis.

We expect two potential confounding factors for the co-primary endpoints: 1) daily salt intake and 2) loss of IV access reducing the amount of IV furosemide given. Any patient with >5g salt intake per day or <20 hours of furosemide per day will be removed from the analysis.

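### One unrecorded fluid day drops a patient still on treatment from the four-day net fluid loss analysis, although a model on the daily values would keep almost all of that patient's information

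*Protocol*

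**What the plan says.** Section 3.4 defines the fluid co-primary as "Difference in mean net fluid loss daily and over a 4 day period". The other co-primary is the change in serum chloride from day 1 to day 4.

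Four statements fix how incomplete fluid data are handled:

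- Section 10.3.2: "any patient with missing data for each of the co-primary endpoints will be excluded from the analysis".
- Section 10.7 counts "those with data on net fluid loss missing on any day" as missing, and lists this separately from not completing four days of treatment.
- Section 10.7: "We will not perform any imputation of missing data".
- Section 10.7: "We will attempt to replace any patient with data missing for either primary endpoint". This is an attempt, not a guarantee.

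The analyses in Section 10.3.2 are to "compare the median net fluid loss using independent samples T-test", with a rank test if the data are not normal, and a "linear regression with total net fluid loss from day 1 to day 4 as the dependent variable". The first is run for each day and for the total. The regression uses one total per patient. No model that uses the four daily values together is planned.

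**The concern.** A daily net fluid value needs two ward records: the patient's diet sheet and the nursing record of urine output (Section 11.1). Where there is no catheter, urine is measured by jug (Section 7.8, Visit 1). A four-day total therefore needs eight complete records. One lost sheet or one unmeasured jug makes the total incomplete for a patient who never left treatment. This loss is distinct from withdrawal or early completion.

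The plan's answer is to drop that patient from the total and look for another. The remaining days were measured and carry most of the information about the four-day difference. At stake is power for the fluid co-primary in a trial of 40 to 50 patients, and recruitment effort spent on recovering information that is already on file.

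**Working it through.** **1. The plan's own sample size.** Section 10.1 gives a difference of 500-1000 mL/day, an SD of 500-1000 mL, 80% power, two-sided 5%, and drop-out of 10% and 20%. At matching ends of the ranges, difference/SD = 1.

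- n per arm = 2 × (1.960 + 0.842)² / 1² = 15.70.
- 15.70 × 1.10 = 17.27 and 15.70 × 1.20 = 18.84. Rounded down, 17 + 18 = 35, the stated minimum.
- The t-test solution is 16.7, so 17 evaluable per arm. The planned 40, split 1:1 with the stated drop-out, gives 20 × 0.9 = 18 and 20 × 0.8 = 16, an average of 17.
- At the maximum of 50 (23 + 27), 23 × 0.9 = 20.7 and 27 × 0.8 = 21.6, about 21 per arm.

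**2. Share of patients losing the total.** Let q be the chance that a patient-day is incomplete, independent across days. The protocol gives no rate, so q is an assumption. The share is 1 − (1 − q)⁴.

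**3. Complete-case power.** Two-sample t-test at a difference of one SD, with n × (1 − q)⁴ per arm and no replacement within the stated number. The one-SD difference is taken to apply to the four-day total.

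| q | lose total | n from 17 | power | n from 21 | power |
|---|---|---|---|---|---|
| 0 | 0 | 17.0 | 81% | 21.0 | 89% |
| 1% | 3.9% | 16.3 | 79% | 20.2 | 87% |
| 2% | 7.8% | 15.7 | 77% | 19.4 | 86% |
| 5% | 18.5% | 13.8 | 72% | 17.1 | 81% |
| 10% | 34.4% | 11.2 | 61% | 13.8 | 71% |

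**4. Information kept by a model on the observed days.** With equal daily variances and between-day correlation ρ, a patient with k days carries k/(1 + (k − 1)ρ), against 4/(1 + 3ρ) for a complete patient. For k = 3:

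- ρ = 0: 3/4 = 75%
- ρ = 0.2: 2.143/2.5 = 86%
- ρ = 0.5: 1.5/1.6 = 94%
- ρ = 0.75: 1.2/1.231 = 97.5%

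Under the complete-case rule this patient contributes 0% to the total. Averaging over the number of missing days:

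| q | model, ρ = 0 to 0.75 | complete cases |
|---|---|---|
| 2% | about 98-99% | 92% |
| 5% | about 95-99% | 81% |
| 10% | about 90-99% | 66% |

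Simulated missing-day patterns, with separate means for each arm and day and 16 per arm, gave nearly the same: 96.9%, 98.6% and 99.4% at q = 5% for ρ = 0.2, 0.5 and 0.75. With 17 evaluable per arm, 90-99% of the information at q = 10% corresponds to power of about 76-80%, against 61% for complete cases.

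**5. What Appendix 2 says about ρ.** Only crude values can be derived. From var(k-day total) = k·s²·(1 + (k − 1)ρ), with s = 1432 mL (root mean square of the three TACTICS-HF daily SDs):

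- DOSE high dose, 72 hours: ρ ≈ 0.48
- DOSE low dose, 72 hours: ρ ≈ 0.06 (about 0 to 0.11 over the range of daily SDs)
- UNLOAD, 48 hours: ρ ≈ 0.66

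Within ATHENA-HF, taking SD = IQR/1.349, the 24-hour and 96-hour figures give 0.75, the 24-hour and 72-hour figures 0.51, and the 24-hour and 48-hour figures an impossible 1.13. A range of about 0 to 0.75 is all the table supports, which is why step 4 spans it.

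**The case against.** **There is more slack than the drop-out allowance.** A reader might take 10% and 20% drop-out as the only margin and conclude that power must fall below 80%. The documents do not support that. Section 10.1 raises recruitment to 50 as a contingency, and Section 10.7 adds replacement for this very case. At about 21 evaluable per arm, power stays at 81% with 5% of days missing. This stands as a limit on the harm. It does not remove it: replacement is only attempted, and Section 10.1 already assigns the reserve to salt intake, lost IV access and the per-protocol analysis.

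**Chloride and the observed days may not be lost.** A reader might infer that all three measured days are discarded and that both co-primaries suffer. Section 10.3.2 can be read endpoint by endpoint and analysis by analysis. On that reading a complete chloride pair stays, and the observed days stay in the daily comparisons. Elsewhere replacement does not mean deletion: Section 7.2 and Visits 3 and 4 in Section 7.8 replace patients but retain their data, while Section 9.9 says removal where removal is meant. Loss from the four-day total is clear. The rest is an ambiguity.

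**Missing days may be rare.** These are inpatients seen daily by a study doctor, many perhaps catheterised, and Section 10.7 expects a minor problem. At 1% of days the loss is under two power points. That is fair, but the better method then costs almost nothing.

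**It is a pilot.** Section 4 makes feasibility and tolerability the primary aim, and Section 10.1 concedes a crude calculation. Section 4 nonetheless claims power for both primary endpoints, and a small sample is where unused data cost most.

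**Conclusion.** The point holds as an efficiency weakness in a rule and methods that the protocol itself fixes. A patient on treatment with one unrecorded fluid day is lost from the four-day total. With 17 evaluable per arm this costs about 2, 4, 9 or 19-20 power points at 1%, 2%, 5% or 10% of days missing. With about 21 per arm it costs about 1, 3, 8 or 17 points. A model on the observed days avoids most of this at any correlation from 0 to 0.75.

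The size rests on three assumptions: the missing-day rate, independence of missing days, and a one-SD difference in the four-day total. The direction does not depend on the correlation. Loss of chloride data is possible under the present wording but not established.

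**What to change.** - Analyse daily net fluid loss with a mixed model for repeated measures (arm, day, arm by day) on all observed days. Report the arm difference averaged over the four days, and four times that for the total. The planned salt and furosemide-hours covariates can be added as in the present regression.
- Reword Sections 10.3.2 and 10.7 so that a single missing fluid day removes the patient from neither the fluid model nor, when both chloride values exist, the chloride analysis.
- Do not replace patients for a single missing fluid day.

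The cost is a wording change and slightly more analysis work, with no new data, visits or patients. The model assumes that a missing day is missing at random given the observed days. That is plausible for an unrecorded volume in a patient still on treatment, and generally weaker than what complete-case exclusion needs.
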